6.3 Lifestyle and/or Dietary Requirements

Throughout the study, subjects may undergo medical assessments and review of compliance with requirements before continuing in the study.

6.3.1 Meals and Dietary Restrictions

Subjects will only consume meals provided by the CRU during inpatient study days. Otherwise, subjects will maintain their own dietary habit during the study.

6.3.2 Caffeine, Alcohol, and Tobacco

Consumption of caffeine- and xanthine-containing products is allowed provided that the subject's consumption has been consistent for the past 30 days. However, during the inpatient days, consumption of caffeinated drinks may be limited to 2 servings each day.

Subjects will not be permitted to consume alcohol from 48 hours before each visit/admission until discharge from the CRU. When not resident in the CRU, male subjects should be advised to limit alcohol consumption to no more than 21 units per week, and female subjects to no more than 14 units per week. All subjects should be advised to limit alcohol consumption to no more than 3 units in a day and not to exceed their habitual alcohol consumption during the study.

Subjects will not be permitted to use tobacco-containing products from 48 hours prior to admission or outpatient visits to the CRU until discharge from the CRU.

6.3.3 Activity

Subjects must refrain from strenuous exercise throughout the study.

6.3.4 Blood Collection

Blood collection via venous catheter during inpatient days.

6.3.5 Male Contraceptive Requirements

Male subjects, regardless of their fertility status, with non-pregnant female partners of childbearing potential must agree to either remain abstinent (if this is their preferred and usual lifestyle) or use condoms as well as one additional highly effective (less than 1% failure rate) method of contraception (such as combination oral contraceptives, implanted contraceptives, or intrauterine devices) or effective method of contraception (such as diaphragms with spermicide or cervical sponges) for 90 days after study drug dosing.

Men and their partners may choose to use a double-barrier method of contraception. Barrier protection methods without concomitant use of a spermicide are not an effective or acceptable method of contraception. Thus, each barrier method must include use of a spermicide. It should be noted, however, that the use of male and female condoms as a double barrier method is not considered acceptable due to the high failure rate when these barrier methods are combined.

Male subjects with pregnant partners should use condoms during intercourse for the duration of the study and until the end of estimated relevant potential exposure in women of childbearing potential, predicted to be 90 days following last dose of study drug.

Male subjects should refrain from sperm donation for the duration of the study and until 90 days following last dose of study drug.

Male subjects who are in exclusively same sex relationships (as their preferred and usual lifestyle) are not required to use contraception.

6.4 Screen Failures

Individuals who do not meet the criteria for participation in this study (screen failure) may not be re-screened, although screening tests such as labs, vital signs / ECGs may be repeated at the discretion of the investigator. Subjects who meet the enrollment criteria, yet are not enrolled within 28 days may be enrolled on a later date, as long as the enrollment criteria are met on Day -1.

7 Treatment

7.1 Treatment Administered

LY3451838 and/or placebo will be administered IV or SC.

Part A: The planned dose levels of LY3451838 are 25 mg, 75 mg, 250 mg, 500 mg, 1000 mg, and 1500 mg. LY3451838 will be administered IV.

After overnight fasting (with water restriction at least 2 hours before dosing), the study drug will be administered as a slow IV infusion over at least 30 minutes for the first 4 cohorts, or over at least 60 minutes for cohorts 5 and 6. Infusion duration may be increased or stopped as deemed necessary based on the standard operation procedure, or if an infusion reaction is observed (Section 7.4.3.2). Sites must have resuscitation equipment, emergency drugs, and appropriately trained medical staff available during the infusion and for at least 6 hours after subjects have completed their infusion. The actual start and stop time of infusion will be recorded in the electronic data capture (EDC). If the infusion is terminated early, this will also be recorded in the EDC. Subject may resume water at least 1 hour after the infusion is completed, and resume meals at least 2 hours after the infusion is completed.

Section 7.4 details dose modifications.

Part B: The planned dose level of LY3451838 in Part B is 250 mg. The dose may be adjusted based on all available data from first 3 cohorts of Part A, the SC dose is intended to match the dose of Cohort 3 in Part A. After overnight fasting (with water restriction at least 2 hours before dosing), the study drug will be administered SC in the abdominal area. Subject may resume water at least 1 hour after the injection is completed, and resume meals at least 2 hours after the injection is completed. Subcutaneous injections should be administered to the abdominal region approximately 5 cm from the umbilicus and the treatment administered with the needle applied at an appropriate angle, with pinching of the skin if necessary. Sites must have resuscitation equipment, emergency drugs, and appropriately trained personnel available for at least 6 hours after subjects have completed their dosing. The actual dosing time will be defined as the time that the injection starts, and will be recorded in the EDC. Only a limited number of individuals will perform SC administration of LY3451838 for consistency reasons. The same type of syringe and needle should be used for all subjects to ensure that injections are delivered to a consistent depth target into the SC space.

LY3451838 Drug Product is a monoclonal antibody formulated for IV or SC administration. LY3451838 for Injection is supplied for clinical trial use as a solution in a single-use glass vial. The vial is manufactured to deliver 200 mg of LY3451838 at 50 mg/mL or 100 mg/mL. In order to ensure complete withdrawal and delivery of the label amount of 200 mg of LY3451838, vials contain an approximate 10% volume overfill. The drug product is filled into a glass vial, and sealed with a stopper and flip-off 2 piece aluminum seal. LY3451838 for Injection vials are stored in refrigerated condition (2°C to 8°C).

This study is double-blinded and the placebo prepared at the site by unblinded dispensing personnel will be 0.9% sodium chloride for injection, BP. This solution is indistinguishable in

appearance from the reconstituted active drug solution. Study drug preparation will be conducted and verified by unblinded personnel. Study drug will be administered by blinded personnel.

The unblinded dispensing personnel will receive training and instructions for preparation of each dose of LY3451838 and the preparation of the placebo solutions.

The investigator or designee is responsible for:

- explaining the correct use of the study drug to the subjects
- verifying that instructions are followed properly
- maintaining accurate records of study drug dispensing and collection
- and returning all unused medication to Lilly or its designee at the end of the study

Note: In some cases, sites may destroy the material if, during the investigative site selection, the evaluator has verified and documented that the site has appropriate facilities and written procedures to dispose of clinical materials.

7.1.1 Packaging and Labeling

The drug product will be manufactured, tested, packaged, and labeled in accordance with all applicable Good Manufacturing Practice (GMP) requirements and country's regulatory requirements. A certificate of analysis confirming the materials are released for human use in clinical trials will be supplied. LY3451838 drug products are for investigational use only and are to be used only within the context of this study.

7.2 Method of Treatment Assignment

In both parts of the study, within each cohort, eligible subjects will be enrolled sequentially, and will be randomly assigned to receive either LY3451838 or placebo in a 6:2 ratio. Treatment assignment will be determined by a computer-generated randomization sequence using an interactive web response system (IWRS).

7.2.1 Selection and Timing of Doses

The single dose of the study drug will be administered at the CRU by a trained staff member.

7.3 Blinding

The study is double-blinded; subjects, investigator, and CRU personnel performing trial-related activities or with the ability to influence study outcomes will be blinded with respect to LY3451838 and placebo treatment. To preserve the blinding, only a minimum number of Lilly personnel may have access to the randomization table and codes or IWRS before the study is complete. Site staff who are responsible for drug preparation will not be blinded; laboratory personnel will also not be blinded.

Emergency unblinding will be performed through the IWRS. This option may be used only if the subject's well-being requires knowledge of the subject's treatment assignment. All unblinding events will be recorded and reported by the IWRS.

In case of an emergency, the Investigator has the sole responsibility for determining if unblinding of a subject's treatment assignment is warranted for medical management of the event. The subject's safety must always be the first consideration in making such a determination. If the Investigator decides that unblinding is warranted, it is the responsibility of the Investigator to promptly document the decision and rationale and notify Lilly as soon as possible.

If a subject's study treatment assignment is unblinded, the subject must be discontinued from the study, unless the Investigator obtains specific approval from a Lilly medical monitor for the study participant to continue in the study. During the study, emergency unblinding should occur only by accessing the IWRS.

7.4 Dose Modification

Dose levels, sampling schedule, timing of procedures (e.g., time of PK sample collection, ECGs) may be adjusted in view of emerging safety or PK data during the study. If considered appropriate, previous dose levels may be repeated, or lower/intermediate dose levels may be tested. The magnitude of the dose escalation may be reduced after data review. Since these adjustments to timings or dose levels are allowable changes permitted by the protocol, they will not require a protocol amendment.

A Safety Review Panel (SRP), comprising experts in early phase medicine independent of the study team and investigative site, will be established by the sponsor. Any changes to the protocol planned dose levels, together with the supporting data, will be reviewed and approved by the SRP before implementation.

7.4.1 Dose Escalation in Part A

Safety and PK data will be the primary criteria for the dose escalation. In addition, if available at the time of dose escalation decision, antidrug antibody (ADA) data will be used as supporting data for dose escalation, but such data are not required. No dose decision can occur without prior discussion and agreement between the investigator and the Lilly medical monitor.

Six dose levels are planned for Part A. Safety data up to Day 15 and PK data up to Day 2 from at least 5 subjects who received LY3451838 and 1 subject who received placebo will be reviewed before each dose escalation decision can be made.

After review of these data, an agreement on the appropriate dose will be made by the investigator and sponsor for the next cohort/dose level. The magnitude of dose escalations may be adjusted following data review. The dose will not exceed 1500 mg.

7.4.1.1 Stopping Rules

If any of the following occur, dosing at the current level and further dose escalation will be discontinued:

1. A single subject experiences an SAE that is related to LY3451838

- a. If an SAE occurs during the infusion of study drug, irrespective of causality, the study drug is discontinued immediately in that subject. No redosing or completion of dosing is considered for that subject regardless of causality. If the infusion SAE is considered related to LY3451838, then the remaining subjects in that cohort are not dosed.
2. Two or more cumulative subjects develop clinically significant acute infusion AEs considered related to LY3451838 during or within 6 hours of completing the infusion that do not resolve with a reduced infusion rate and/or supportive care.
3. Two or more cumulative subjects develop clinically significant hypersensitivity AEs considered related to LY3451838
4. Two or more cumulative subjects experience similar clinically significant events (CSEs) considered related to LY3451838. A CSE will be defined as a moderate-to-severe AE, abnormal clinical sign, or clinical laboratory finding that may pose a risk to the well-being of the subject.
5. 50% or more subjects at a dose level experience moderate or severe AEs that impair normal activities, but do not meet the CSE criteria, and are considered related to LY3451838.

Two or more subjects experience severe adverse reactions, irrespective of their nature.

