5.1 Overall Design

[figure not shown]
Study J1H-MC-LAJA is a first-in-human, Investigator- and subject-blind, placebo-controlled, randomized study in healthy subjects to evaluate the safety, tolerability, and pharmacokinetics of LY3451838.

The study will be comprised of 2 parts: Part A (single ascending dose with IV administration), and Part B (single dose SC administration). Part B of the study will only be initiated if the review of safety and tolerability data from Part A are supportive.

Screening will occur in the 28 days prior to Day 1. Eligible subjects will be assigned sequentially into up to 8 cohorts, and randomly assigned within each cohort to receive LY3451838 or placebo in a 6:2 ratio. Subjects will be followed for safety / tolerability, PK and immunogenicity, and will be discharged from the study approximately 20 weeks after dosing. If the investigator decides not to administer the first dose to a subject or not to enroll a subject on a particular day, the subject may be rescheduled to participate in the study and any procedures performed up to that point may be repeated. Subjects who discontinue from the study (Section 8.2) before its completion are required to complete the early discontinuation (ED) procedures (Section 2) before their discharge from the study.

Figure 5.1.

Illustration of study design for Protocol J1H-MC-LAJA.

Abbreviations: D = day; W = week

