All parts of the study will be placebo-controlled. Study participants and investigators will be blinded to treatment assignment. This design allows for a more objective assessment of AEs, and enables a comparison of the safety profile between different treatment groups. The sponsor will not be blinded to the treatment assignment to enable prompt management of any emergent safety trend and to perform periodic review of PK and immunogenicity data. Plans to maintain the blind are discussed in Section 7.3.

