9.2.1 Serious Adverse Events

An SAE is any AE from this study that results in one of the following:

- death
- initial or prolonged inpatient hospitalization
- a life-threatening experience (that is, immediate risk of dying)
- persistent or significant disability/incapacity
- congenital anomaly/birth defect
- important medical events that may not be immediately life-threatening or result in death or hospitalization but may jeopardize the subject or may require intervention to prevent one of the other outcomes listed in the definition above.

The CRU personnel must alert the Lilly medical monitor, or its designee, of any SAE as soon as practically possible.

Additionally, CRU personnel must alert Lilly Global Patient Safety, or its designee, of any SAE within 24 hours of Investigator awareness of the event via a Sponsor-approved method. If alerts are issued via telephone, they are to be immediately followed with official notification on study-specific SAE forms. This 24-hour notification requirement refers to the initial SAE information and all follow-up SAE information.

Although all AEs are recorded in the case report form or EDC after signing informed consent, SAE reporting to the Sponsor begins after the subject has signed informed consent and has received the study drug. However, if an SAE occurs after signing informed consent, but prior to receiving the study drug, AND is considered Reasonably Possibly Related to a study procedure then it MUST be reported.

Investigators are not obligated to actively seek AEs or SAEs in subjects once they have discontinued from and/or completed the study. Serious adverse events will be collected for

30 days after the last dose of study drug. However, if the Investigator learns of any SAE, including a death, at any time after a subject has been discharged from the study, and he/she considers the event reasonably possibly related to the study treatment or study participation, the Investigator must promptly notify Lilly.

Pregnancy (maternal or paternal exposure to the study drug) does not meet the definition of an adverse event. However, to fulfill regulatory requirements any pregnancy should be reported following the SAE process to collect data on the outcome for both mother and fetus.

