Dose proportionality for exposure (AUC, C_{max}) may be assessed using the power model approach, as appropriate. Additional analyses may be performed if deemed necessary.

10.3.3 *Exploratory Pharmacodynamic Analyses*

Summary statistics for each exploratory endpoint may be provided by dose level and time for subjects randomized to LY3451838 and for all placebo subjects combined. Additional analyses may be conducted as appropriate.

10.3.4 *Evaluation of Immunogenicity*

The frequency and percentage of subjects with preexisting ADA and with TEADA+ to LY3451838 will be tabulated. Treatment-emergent ADAs are defined as those with a titer 2-fold (1 dilution) greater than the minimum required dilution if no ADAs were detected at baseline (treatment-induced ADA) or those with a 4-fold (2 dilutions) increase in titer compared to baseline if ADAs were detected at baseline (treatment-boosted ADA). For the TEADA+ subjects, the distribution of maximum titers will be described. The frequency of neutralizing antibodies may also be tabulated in TEADA+ subjects.

The relationship between the presence of antibodies and the PK parameters and PD response including safety and efficacy to LY3451838 may be assessed.

10.3.5 *Data Review During the Study*

Interim access to safety data is scheduled to occur throughout the study. The investigator and the Lilly medical monitor will make the determination regarding dose escalation based on their review of the blinded safety, tolerability and PK data. Review of ADA data is scheduled on a

rolling basis throughout the study to guide dose selections. Individual PK/PD/ADA data will not be reviewed by the investigator until the study is complete to avoid unblinding. A small number of individuals from Lilly sponsor team will be unblinded during these reviews.

10.3.6 *Interim Analyses*

At least 1 interim analysis is planned for this study. It will be conducted after the 12-week ADA data from the first two cohorts are available. All available safety, tolerability, PK and ADA data up to that point will be reviewed by the sponsor. The interim analysis will be used to guide the design of this and subsequent studies.

Additional interim analyses may be conducted without protocol amendment, as the primary objective for this study is not based on inferential statistical analyses. No adjustments for multiple comparisons will be made.

11 References

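### Stopping items 4 and 5 leave a narrow gap: related, moderate, non-serious CSEs of different kinds trigger no automatic stop at any count, whereas as many lesser AEs do.

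*Protocol*

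**What the plan says.** Protocol 7.4.1.1 lists events after which dosing at the current level and further escalation are discontinued.

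- Item 1: one related SAE.
- Items 2 and 3: two or more cumulative subjects with related acute infusion AEs that do not resolve, or with related hypersensitivity AEs.
- Item 4: "Two or more cumulative subjects experience similar clinically significant events (CSEs) considered related to LY3451838". A CSE is a moderate-to-severe AE, sign or laboratory finding that could put the subject's well-being at risk.
- Item 5: "50% or more subjects at a dose level experience moderate or severe AEs that impair normal activities, but do not meet the CSE criteria", where the AEs are considered related to LY3451838.
- Unnumbered last line: "Two or more subjects experience severe adverse reactions, irrespective of their nature".

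Each cohort has 6 active and 2 placebo subjects (5.1). Item 5 does not say whether its percentage is of the 6 or of the 8. Nothing in the section defines when two CSEs are similar.

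Outside the stopping rules, 7.4.1 requires a data review before each escalation: "After review of these data, an agreement on the appropriate dose will be made by the investigator and sponsor for the next cohort/dose level". Section 5.4 adds: "The sponsor will not be blinded to the treatment assignment to enable prompt management of any emergent safety trend".

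**The concern.** Item 5 is the only rule based on a proportion of subjects, and it leaves out the events that the protocol itself ranks as more worrying. If an AE is reclassified upward to a CSE, it drops out of the item 5 count and counts elsewhere only if it resembles another CSE, is serious, is one of two severe reactions, or falls under items 2 or 3.

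At one dose level, half the active subjects could therefore have related moderate CSEs, each of a different kind, with no mandatory stop, while the same number of lesser AEs would force one. In a first-in-human study, the decision for the more worrying pattern is left to judgement. Part B is affected too, because 7.4.2 ties its start to whether these same rules were met in the first three cohorts.

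**Working it through.** The plan states no operating characteristic for these rules, so there is no figure to reproduce. The check has two parts: the logic of the text, which needs no assumptions, and an illustration of size, which does.

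**1. Logic.** Apply the rules to *n* of 6 active subjects, each with one related, non-serious AE that impairs normal activities and is neither an infusion nor a hypersensitivity event.

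| Events | First stop |
|---|---|
| Moderate CSEs, similar | n = 2 (item 4) |
| Severe CSEs, different kinds | n = 2 (last line) |
| Moderate AEs, not CSEs | n = 3 (item 5, denominator 6) or n = 4 (denominator 8) |
| Moderate CSEs, different kinds | none, up to n = 6 |
| 2 non-CSE AEs plus 2 CSEs of different kinds, all moderate | none |

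The fourth row against the third is the gap. It is present under either denominator.

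**2. Size, given the events.** Assumptions, none from the documents: *k* kinds of CSE, a share *q* of CSEs that are SAEs, and a share *s* of AEs that are severe. For *n* CSEs:

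P(no stop) = P(all kinds differ) × (1 − q)^n × P(fewer than 2 severe)

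For n = 3 and q = s = 0:
- k = 5: 5·4·3/125 = 0.480
- k = 10: 10·9·8/1000 = 0.720
- k = 20: 20·19·18/8000 = 0.855

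For n = 3 and k = 10, with adjustments added in turn:
- One kind takes 40% of CSEs and the other nine share the rest: 0.6³ × (9·8·7/9³) + 3 × 0.4 × 0.6² × 8/9 = 0.149 + 0.384 = 0.533
- Also q = 0.2: 0.533 × 0.8³ = 0.273
- Also s = 0.2: 0.273 × (0.8³ + 3 × 0.2 × 0.8²) = 0.273 × 0.896 = 0.245

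Earlier CSEs shrink the gap because item 4 is cumulative. With k = 10 and no adjustments, one earlier CSE gives 9·8·7/1000 = 0.504, and two of different kinds give 8·7·6/1000 = 0.336.

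For the mixed cohort (2 + 2), k = 10 gives 0.900. With all three adjustments it is 0.8 × 0.64 × 0.819 = 0.419.

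**3. How often the events arise.** If each active subject has probability *p* of such a CSE, the binomial chance of 3 or more in 6 is 0.016 at p = 0.1, 0.099 at 0.2, 0.256 at 0.3 and 0.656 at 0.5. Multiplying by the range 0.245 to 0.720 gives a per-cohort chance of the pure-CSE gap of about 0.4% to 1.1% at p = 0.1 and 2.4% to 7.1% at p = 0.2. These are slightly high, since four or more CSEs are more likely to include a similar pair. Mixed cohorts add to them.

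**4. Effect of counting CSEs in item 5 at 3 of 6.** Simulation with k = 10 and one AE per subject; every non-CSE AE impairs normal activities; items 2 and 3 and placebo events are left out. The added chance of a stop over six cohorts ranges over CSE shares of 50% and 100%, with and without the three adjustments:

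| AE rate per subject | Added chance, percentage points | Upper end if the text now means 4 of 8 |
|---|---|---|
| 5% | 0.1 to 1 | 1 |
| 10% | 0.3 to 5 | 6 |
| 20% | 0.2 to 16 | 21 |

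**The case against.** A reader might infer that the rules as a whole are inverted. They are not. One related SAE stops dosing, as do two similar CSEs across cohorts or two severe reactions of any kind, whereas lesser AEs need half a dose level. The gap needs several CSEs with none serious, at most one severe, and each different from the others and from any earlier CSE.

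Item 1 may also absorb much of it. SAEs include "important medical events that may not be immediately life-threatening or result in death or hospitalization but may jeopardize the subject" where intervention may be needed, which lies close to the CSE definition. The 20% overlap used above is a guess. At 50%, the 3-of-6 figure falls to 0.720 × 0.5³ = 9%. A broad reading of similarity, for example by organ system, shrinks the gap further. Asking for similar events is itself reasonable, because repeated like events point to the drug more clearly than scattered ones.

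A reader might also infer that dosing would go on unchecked. The documents do not support that. Sentinel data through Day 5 are reviewed before the rest of a cohort is dosed (5.1.1). Escalation needs the agreement of the investigator and the medical monitor (7.4.1), and the sponsor is unblinded. Part B has a further condition: "Part B of the study will only be initiated if the review of safety and tolerability data from Part A are supportive".

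All of this stands as a limit on size. It does not close the gap. A floor meant for lesser events has no reason to exclude worse ones, and review is a judgement where 7.4.1.1 would otherwise require a stop.

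**Conclusion.** The gap follows from the text alone and rests on no assumed rate. It is narrow, and only the automatic trigger is lost. The ambiguous denominator in item 5 is a second, smaller defect in the same sentence.

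No figure above is an estimate for this trial. The documents give no event rates and no definition of similarity, and the amendment (d) summary reports no SAEs and no AE discontinuations in 40 subjects up to 1000 mg. That gives no support for assuming that half a cohort would have moderate related events. The change is still worth making, because a first-in-human stopping rule should not become less binding when an event is judged more worrying, and the correction is cheap.

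**What to change.** Replace item 5 of 7.4.1.1 with:

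> At least 50% of the planned LY3451838 subjects at a dose level (3 of 6) experience moderate or severe AEs that impair normal activities or meet the CSE criteria, and are considered related to LY3451838.

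Keep the similarity requirement in item 4, so that two unlike CSEs do not by themselves end escalation. Replacing the exclusion, and not merely deleting it, means that CSEs which do not impair activities are counted too, such as laboratory findings, which the AE definition in Appendix 1 includes. The fixed count of 3 of 6 matters because of sentinel dosing: a percentage of active subjects dosed so far would let one event in the single active sentinel subject count as 100%.

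The cost is one sentence in an amendment and no new data. Because the investigator is blinded, the count of active subjects falls to sponsor staff already in place (10.3.5): "A small number of individuals from Lilly sponsor team will be unblinded during these reviews". The downside is the added chance of a stop tabulated above, which is small at low AE rates but not negligible at 20%. Each added stop falls at a dose level where at least half the active subjects have a related moderate or severe event. If the present text means 4 of 8, the change also lowers the threshold, and the sponsor should make that choice knowingly.
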